### **1.6.4 Adverse Reaction Risk Management**

Investigators and all study personnel will be trained in the details of all aspects of the study procedures. Standardization of topical drug and placebo application techniques is critical to a good clinical outcome. To minimize risks and increase the chances of a favorable clinical outcome the following measures are required:

- Subjects will be educated on treatment application during pre-operative visit
- Potential risks will be listed in the patient consent form and quantified during the course of treatment via patient questionnaires (VSS and POSAS)
- Follow-up will continue for 3 months following surgery: in-person appointments with study staff will occur during treatment period at 2 weeks and 4 weeks after surgery. A final visit will be encouraged at 3 months after surgery. A follow-up phone call will be made by study staff 24 hours after surgery and postoperative weeks 1 and 3, and month 2 (and 3 if the patient is unable to return for in-clinic follow-up).

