**Visit #5: (Month 3 postop)**

[figure not shown]
- Scar photography
- Quality questionnaires (VSS and POSAS)
- Assessment of adverse events
- Note: if the patient is unable to return for an in-clinic appointment, a phone interview will be conducted

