### 3.4 Primary Study Endpoints

**Aim #1:** Identify the type and number of serious adverse events related to TP in PCCA PP compared to PCCA PP base alone following surgical scar excision. While we do not anticipate any severe adverse events, we will monitor for the following:

- Skin infection
- Skin irritation
- Wound dehiscence
- Clinically significant abnormalities in physical examination and vital signs.

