### 3.6 Identification of Source Data

The following source data will be directly recorded on the Case Report Form (CRF):

- Patient demographic data:
  - Age
  - Sex
  - Ethnicity
  - Indication for scar excision
  - Concomitant medications
- Inclusion criteria
- Exclusion criteria
- Physical examination
- Trial medication administration
  - Date of dosing
  - Time of dosing
- Assessment

- POSAS
- VSS
- Adverse events
  - Pain
  - Rash
  - Skin Ulcer
  - Erythema
  - Pruritus
  - Urticaria
  - Erosions
  - Scabbing
  - Infection
  - Depigmentation
  - Hypopigmentation
  - Hyperpigmentation

The following source data will not be directly collected in the Case Report Form (CRF), but will be captured in supportive documentation (EMR):

- Photographs of lesion area
- Ultrasound 3D radiographic images
- Histology report from 5-mm skin biopsy

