## **6.10 Visit #5: (Month 3 post op)**

The scar will be photographed and quality questionnaires (VSS and POSAS) will be completed. Patients will be assessed for any adverse events.

Range for phone interviews for call 2 and 3: +/- 1 day

Range for phone interview for call 4: +/- 1 week

Range for study visits 3 and 4: +/- 1-3 days

Range for study visit 5: +/- 2 weeks

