## 6.11 Schedule of Events

Study Activity	Schedule of Events									
	Visit 0 Pre-op	Visit 1 Pre-op	Visit 2, Week 0, Day 0 Surgery	Phone 1, Week 0, Day 1	Phone 2 Week 1	Visit 3, Week 2	Phone 3 Week 3	Visit 4, Week 4	Phone 4, Month 2	Visit 5 Month 3
Informed consent	X									
Randomization		X								
General evaluation, physical exam and vital signs a		X								
Scar photography		X	X			X		X		X
Neuropsychiatric exam and local safety evaluation (baseline and adverse event assessment) b		X				X		X		
Laboratory studies c		X				X		X		
Quality questionnaires (VSS and POSAS) d		X				X		X		X
US and/or 3D imaging e		X				X		X		
Cardiac monitoring (ECG) f		X				X		X		
Treatment application patient education		X								
Dispense study drug g			X			X				
Surgical scar excision			X							
5-mm skin punch biopsy		X						X		
Phone interview				X	X		X		X	
Adverse event evaluation				X	X	X	X	X	X	X

a: Vital signs include blood pressure, pulse, temperature and respiratory rate. Physical exam includes skin check.  
b: Clinical exam for neuropsychiatric exam will include evaluation for confusion and hallucination.  
c: Hepatic and renal function, complete blood count with differential, blood glucose level and calcium  
d: Quality questionnaires: Vancouver Scar Scale (VSS) and Patient Observer Scar Assessment Scale (POSAS).  
e: Ultrasound (US) and/or 3D-scanner imaging used to evaluate scar height.  
f: Safety evaluation will include cardiac monitoring with electrocardiogram (ECG).  
g: Single dose containers with de-identified treatment agents (active topical drug and silicone-base only).

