## Adverse Event

An untoward or undesirable experience associated with the use of a medical product (i.e. drug, device, biologic) in a patient or research subject.

The safety evaluation of this topical drug product during the conduct of a clinical trial includes an assessment of systemic safety as well as evaluation of local safety. Evaluation of systemic safety addresses warnings, precautions, and adverse events from approved product labeling for pentamidine isethionate (e.g., laboratory studies including renal and hepatic function, hematology, blood glucose, and calcium; periodic cardiac monitoring with electrocardiogram [ECG], and assessment for neuropsychiatric adverse events [including confusion and hallucinations]. The evaluation of systemic safety will be conducted at baseline (Visit 1, pre-operative), during treatment (Visit 3, Week 2), and after treatment (Visit 4, Week 4) and extended follow-up (Visit 5, Month 3). The local safety evaluation includes an active assessment of local tolerability (e.g. erythema, edema, vesication, necrosis, ulceration etc.) using an acceptable scale called the local skin reaction (LSR) grading scale [30]. The LSR grading scale uses a 0-4 numerical rating, with clinical descriptor and representative photographic images for each rating. The scale provides the ability to rate each LSR category (erythema, flaking/scaling, crusting, swelling, vesication/postulation and erosion/ulceration) and generate a composite objective LSR score [30].

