## Adverse Event Reporting Period

For this study, the study treatment follow-up period is defined as 3 months following the last administration of study treatment.

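### Vital signs are scheduled only before surgery, the stated Month 3 systemic safety evaluation has no scheduled tests, and the reporting period outlasts the last planned contact by a nominal 27–31 days

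*Combined protocol and SAP*

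**What the plan says.** **Vital signs.** Section 3.4 sets the primary aim as serious adverse events related to the active gel compared with the base alone. Among the items to be watched for, it lists "Clinically significant abnormalities in physical examination and vital signs". In Section 6.11 the row "General evaluation, physical exam and vital signs" has a single mark, at Visit 1 before surgery. Its footnote defines vital signs as blood pressure, pulse, temperature and respiratory rate.

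**Month 3 systemic evaluation.** Section 8.1 (Adverse Event) describes systemic safety evaluation by laboratory tests, ECG and neuropsychiatric assessment. It places this at baseline, at Week 2, "and after treatment (Visit 4, Week 4) and extended follow-up (Visit 5, Month 3"). Section 6.10 gives the content of Visit 5 as: "The scar will be photographed and quality questionnaires (VSS and POSAS) will be completed. Patients will be assessed for any adverse events". The treatment schema in Section 3.1 adds that "if the patient is unable to return for an in-clinic appointment, a phone interview will be conducted".

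**End of follow-up.** Under the heading Adverse Event Reporting Period, Section 8.1 states that "the study treatment follow-up period is defined as 3 months following the last administration of study treatment". Section 1.6.4 counts from surgery instead: "A final visit will be encouraged at 3 months after surgery".

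**The concern.** Safety is the primary objective, and the plan describes the study as the first in humans. In three places it promises safety observations that its own schedule does not provide.

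If the schedule is followed as written, a report that no vital-sign abnormality occurred after dosing would rest on whatever staff happened to measure. A report of systemic safety at Month 3 would rest on adverse event questions, with no scheduled laboratory test or ECG after week 4.

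The pharmacokinetics text in Section 5.1 shows why late testing could matter. For systemic drug it gives a terminal half-life of 2–4 weeks, urinary excretion for up to 8 weeks after stopping, and possible accumulation on repeated dosing. The documents give no figure for absorption from the gel, so actual exposure is unknown.

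The reporting period also has practical force. Section 8.2 requires immediate reporting of possibly related serious events that occur within it.

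**Working it through.** **Vital signs.** The visit texts were read against the schedule.
- Visits 3 and 4 (Sections 6.6 and 6.8) list a clinical exam, local tolerability, neuropsychiatric assessment, laboratory tests and ECG. Neither names vital signs.
- Visit 5 (Section 6.10) lists photography, the two scar scales and adverse events.
- The only vital-signs mark in Section 6.11 precedes surgery, and dosing starts 24 hours after surgery.
- Scheduled vital-sign measurements after the first dose: 0.

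**Systemic tests after week 4.** In Section 6.11 the laboratory, ECG and neuropsychiatric rows are marked at Visits 1, 3 and 4 only. Tests scheduled after Visit 4: 0, against one evaluation stated for Month 3.

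Visit 4 is nominally day 28, with a window of up to 3 days either side (days 25–31). The last application falls on days 27–31, as shown below. The final tests therefore coincide roughly with the last application and can precede it.

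**Reporting period.** Inputs:
- first application on day 1, then every 2 days (Section 5.2)
- 14–16 applications (Section 3.1); 14 in Section 5.3
- 8 containers per site at each of two dispensations, so 2 × 8 = 16 (Section 5.5)
- Visit 5 at Month 3 after surgery, ± 2 weeks (Section 6.10)
- assumption: 3 months = 91 days

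The plan's own application count is reproduced first. Every second day from day 1 to day 28 gives 14 applications, the last on day 27. The 16 dispensed containers give the upper figure.

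Day of application n = 1 + 2(n − 1). End of period = that day + 91. Visit 5 is nominally day 91, with window 91 ± 14 = days 77–105. Gap = end of period − day of Visit 5.

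| Applications | Last application (day) | Period ends (day) | Gap, visit on day 105 | Gap, visit on day 91 | Gap, visit on day 77 |
|---|---|---|---|---|---|
| 14 | 27 | 118 | 13 | 27 | 41 |
| 15 | 29 | 120 | 15 | 29 | 43 |
| 16 | 31 | 122 | 17 | 31 | 45 |

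As shares of the 91-day period:
- nominal: 27/91 = 29.7% to 31/91 = 34.1%
- full window: 13/91 = 14.3% to 45/91 = 49.5%

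With any fixed length for 3 months, the nominal gap equals the day of the last application, because the same length is added to both start points. With true calendar months over 1,461 surgery dates, the averages stay at 27, 29 and 31 days, and single dates range from 25 to 34.

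**The case against.** **Vital signs.** The formal endpoint is related serious adverse events, and vital signs are half of one monitoring item. An ECG at Visits 3 and 4 normally yields a heart rate, and Section 1.6.1 covers fever by phone questions and self-monitoring. A clinical exam does take place after dosing, so the physical-examination half of the item is covered. This is fair and narrows the point. It does not supply a scheduled set of vital signs, and blood pressure and respiratory rate have no substitute at all. The source-data lists in Section 3.6 also omit vital signs, but they omit laboratory tests and ECG too, so that omission carries little weight.

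**Month 3.** Section 8.1 introduces its tests as examples and does not say that every test is done at every time point. An adverse event interview, even by phone, could pick up confusion or hallucinations. Visit 4 tests also fall near the end of exposure, when any accumulation should be close to its greatest. All of this has some force. Even so, the neuropsychiatric row is unmarked at Visit 5, a phone call cannot deliver laboratory tests or an ECG, and slow elimination is itself a reason to look after week 4.

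**Reporting period.** A reporting duty may outlast the last planned contact. Section 8.1 (Post-study Adverse Event) tells subjects to report later events they think may be related, and unresolved events are followed. That is a partial safeguard, but new events in the gap are then captured only if the subject comes forward. The upper end of 27–31 days depends on 15 or 16 applications, which end on days 29 and 31, past a 4-week count from surgery. With 14 applications the gap is 27 days. The range is the plan's own, and the differing application counts also need reconciling.

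**Conclusion.** The concern holds in all three parts.
- **Vital signs:** none are scheduled after dosing, although they are named under the primary safety aim.
- **Systemic tests:** none are scheduled after week 4, although an evaluation is stated for Month 3. Adverse events are still asked about at Months 2 and 3, so what is missing is testing.
- **Reporting period:** it ends a nominal 27–31 days (30–34% of 91) after the last planned contact. Across the permitted Visit 5 window the gap is 13–45 days (14–49%).

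The day counts assume that applications run on schedule from day 1 and that 3 months is 91 days.

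The consequence is limited to patient-level systemic safety conclusions. Each patient receives both gels, so systemic findings could not separate them in any case, and the comparison of the two scar sites is not biased.

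**What to change.** Reconcile three sets of passages. In each, either the text or the schedule can move.

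1. **Sections 3.4 and 6.11.** Either mark vital signs at the existing clinic visits after dosing (Visits 3 and 4, and Visit 5 when attended in person), or remove vital signs from Section 3.4. Measurement takes a few minutes per visit.
2. **Section 8.1 (Adverse Event), the Section 3.1 schema, 6.10 and 6.11.** Either list at Visit 5 the tests that Section 8.1 intends and say what happens when the visit is a phone call, or remove Visit 5 from Section 8.1 and limit the conclusion from systemic tests to week 4. The wording option costs nothing. The testing option is the one material expense: up to 10 laboratory panels, 10 ECGs and 10 neuropsychiatric exams, with attendance in person.
3. **Section 8.1 (Adverse Event Reporting Period), 1.6.4 and 6.10.** Either define the period as ending at Month 3 after surgery, or add a closing phone contact 3 months after the last application. The cost is a wording change or up to 10 calls.

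The wording-only route narrows the stated safety window, and the report should say so. The application counts in Sections 3.1, 5.3 and 5.5 should be reconciled in the same amendment, because they set the end of the reporting period.

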### 3.5 Secondary Study Endpoints

**Aim #2:** Evaluate initial signals of efficacy as measured by US dimensions (length, width and height) and volume quantification, skin biopsy histological features (semi-quantitative assessment of skin fibrosis) and patient-reported outcome metrics (per VSS and POSAS). Preoperative US as well as 2 week and 4 week postoperative US will be compared based on formal quantification of the hypertrophic scar lesion volume size (unit of measure: cm^3). Preoperative 5-mm skin biopsy and 4 week postoperative skin biopsy will be used for histological evaluation (including epidermal hyperplasia/hyperkeratoses, hair follicles, apocrine glands, smooth muscles, fibroplasia, vascular proliferation and collagen orientation) [27] and epidermal scar thickness calculation. Quality of life and scar elevation scores will also be assessed at serial follow-up as measured by VSS and POSAS.

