**Study Summary**

Title	Double Blind, Single-Center, Randomized, Within-Subject Placebo, Phase I Study Evaluating the Effects of Topical Pentamidine in Prevention of Hypertrophic Scar Formation
Running Title	Novel Topical Gel for Hypertrophic Scar Prevention
IRB Protocol Number	17-005230
Phase	Pilot Study
Methodology	Double Blind, Single-Center, Randomized, Within-Subject Placebo Phase I Study
Overall Study Duration	3 months
Subject Participation Duration	3 months
Single or Multi-Site	Single site
Objectives	Evaluate safety of topical pentamidine (TP) as an adjuvant to surgical scar excision (SSE) in the treatment of hypertrophic scar formation. Safety will be measured by serial monitoring for adverse events following the procedure and during treatment duration. Secondarily, study will evaluate drug quality and standardizations as well as investigate initial signs of efficacy.
Number of Subjects	10
Diagnosis and Main Inclusion Criteria	Hypertrophic scar diagnosed in Mayo Clinic Department of Dermatology or Division of Plastic Surgery, Rochester, Minnesota.
Study Product, Dose, Route, Regimen	Pentamidine, delivered as topical formulation containing 2% TP in silicone-containing base, PCCA Pracasil™-Plus (PP), versus placebo base alone. Approximately 1.8 mL of product in allotted single dose containers will be applied every 48 hours for 4 weeks following surgical scar excision.
Duration of Administration	Once every 48 hours for 4 weeks.
Reference therapy	SSE with silicone compounding base only (PCCA PP).
Statistical Methodology	The primary analysis will use descriptive statistics to document adverse events between treated and untreated lesions. The secondary analysis will use paired t-test or Wilcoxon signed rank test to compare the change in lesion height and characteristics between the treated and placebo groups following SSE (TP + PCCA PP vs. PCCA PP alone). In addition, two-factor analysis of variance (ANOVA) with repeated measures on both factors will be used to evaluate the effect of treatment and follow-up time for other continuous measures such as Vancouver Scar Scale (VSS) and Patient and Observer Scar Assessment Scale (POSAS).

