## 3 Study Design

### 3.1 General Description

This study is a double-blind pilot study of scar excision procedure followed by treatment with either TP in PCCA PP versus PCCA PP silicone base only. Current management for patients with hypertrophic scar includes silicone-based treatment. At our institution we treat patients with scar excision surgery without topical scar cream following the procedure. However, a significant proportion of patients continue to fail this treatment modality leading to scar recurrence. Indeed, individual patient response to therapy varies based on patient characteristics including ethnicity. As such, we plan to treat the same patient with both TP in PCCA PP and PCCA PP alone at different ends of their scar. In this way, we can better determine efficacy of these topical agents in biologically controlled setting with reduced response variability. We plan to enroll patients with minimum hypertrophic scar length  $\geq 3$  cm.

Those patients who successfully qualify based on inclusion and exclusion criteria will be invited to participate in the trial. Following informed consent, eligible subjects will undergo pre-operative tests to include blood work and EKG. Preoperative photographs of the scar site will be taken. Scar quality questionnaires (VSS and POSAS) will be completed and a scar ultrasound performed.. A 5-mm skin punch biopsy will be obtained from the lateral edge of the scar at both the proximal and distal ends of the scars, under local anesthesia. Alternatively, the first punch biopsy may occur prior to the surgical procedure while the patient is under anesthesia. Part of the sample will be stored in formalin and prepared for histological staining. The other portion will be frozen and prepared for molecular analysis. All participants will receive both treatments to be applied either at the proximal end or the distal end of the scar. Treatment application will be randomized. For example, topical agent A will be applied to the proximal end of the scar and will contain either TP

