in PCCA PP or PCCA PP. Topical agent B will treat the distal portion of the scar and contain either TP in PCCA PP or PCCA PP alone. 1-2cm in the middle of the scar will remain untreated as the border zone. It is known that blood perfusion influences scar formation; thus to reduce potential bias from distal scar site receiving reduced blood flow compared to proximal scar site, treatment application will be randomized to scar site. Prior to treatment initiation, patients will undergo scar excision procedure with a 24-hour recovery period. Treatments will be provided in single dose containers for application every 48 hours following surgical recovery (total of 14-16 applications; total treatment duration of 4 weeks).

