## 5.2 Treatment Regimen

First dose will be applied 24 hours post-surgical scar excision, then scheduled every 48 hours. Approximately 1.8 mL (0.06 oz) of topical pentamidine (TP) or PCCA PP control will be topically applied via single dose containers provided the day of surgery and at their 2-week postoperative follow-up visit. Participants will receive two sets of single dose containers (set A and set B). One set will be randomized to contain TP with de-identified label; the other set will be randomized to contain PCCA PP with de-identified label. Each set (A and B) will contain 8 single dose containers, all with a de-identified label. The study drug will be applied every 48 hours. Specifically, topical agent (either TP or PCCA PP) will be applied to either the distal or the proximal end of the wound. Study participants will receive treatment application education during their pre-operative visit; further details provided in Section 6.1. Treatment duration is 4 weeks.

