### 6.2 Visit 1 (Preoperative period)

Patients will receive a comprehensive pre-operative evaluation. This evaluation will gather information relating to medical history as well as include a standard clinical exam and necessary laboratory studies. Once consent is provided and patient meets inclusion criteria as a qualified participant for the study, photographs will be taken of the lesion area with a digital camera and/or photography service. Pre-operative ultrasound and/or 3D imaging will also be performed to determine initial scar height and morphology. The scar will be assessed using the Vancouver Scar Scale (VSS) [28] and the Patient and Observer Scar Assessment Scale (POSAS) [29]. These scales will determine the initial level of hypertrophy and scar attributes before treatment initiation. Safety evaluation will include assessment of systemic and local safety and thus baseline clinical exam with neuropsychiatric evaluation, laboratory studies (including hepatic and renal function, complete blood count with differential, blood glucose level and calcium) and baseline cardiac monitoring with electrocardiogram (ECG) will be performed.

This visit will include two 5-mm skin punch biopsy (one from distal site and one from proximal scar site) performed under local anesthesia in a dedicated procedure room. Alternatively, the first punch biopsy may occur prior to the surgical procedure while under anesthesia. This sample will be processed by the study staff for histological/molecular evaluation to analyze scar characteristics.

Patients will also be educated on proper treatment application. Treatment regimen and duration will be summarized. For example, following their surgical scar excision procedure, they will be provided single dose containers with topical study agents. There will be two different formulations given to patients; one is the placebo control (PCCA PP) and the other is the active treatment (TP). Patients and providers blinded to treatment regions but their treatment label will have appropriate instructions for application either at the distal or proximal region.

Based on the distal or proximal region assigned to each formulation by the pharmacist and appropriately labeled single dose containers, patients will apply the unit dose. Compound A (either TP or PCCA PP) will be applied to proximal site and Compound B (either TP or PCCA PP) will be applied to the distal site; 1-2 cm border zone in the middle of the scar will remain untreated.

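### Section 3.5 compares ultrasound of the excised scar with ultrasound of the new wound: within one site this cannot show a drug effect, and as a subtracted baseline it can cost precision

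*Combined protocol and SAP*

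**What the plan says.** Section 3.5 gives the ultrasound comparison for the efficacy aim: "Preoperative US as well as 2 week and 4 week postoperative US will be compared based on formal quantification" of lesion volume. It does not name TP against base as the contrast.

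The order of events is fixed elsewhere. Section 3.1: "Prior to treatment initiation, patients will undergo scar excision procedure with a 24-hour recovery period". Section 5.2: "First dose will be applied 24 hours post-surgical scar excision, then scheduled every 48 hours". Section 6.2 places baseline imaging at Visit 1: "Pre-operative ultrasound and/or 3D imaging will also be performed to determine initial scar height and morphology". The schedule in Section 6.11 has imaging at Visits 1, 3 and 4 only. Section 4.1 requires the scar to have been present for at least 6 months.

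The Study Summary does name a between-treatment contrast. A paired t-test or Wilcoxon signed rank test will "compare the change in lesion height and characteristics between the treated and placebo groups following SSE". It does not say from which measurement the change is taken. Section 7.2 names a paired t-test but gives no endpoint or contrast.

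**The concern.** The pre-operative scan shows a mature scar that is removed before any study product is applied. The Week 2 and Week 4 scans show a new wound in its place. The two readings differ because of the operation as well as anything the gel does, and no post-excision, pre-dose image exists to separate the two.

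Two things are at stake. If the comparison in Section 3.5 is read within a site, base alone could appear to work. If the pre-operative value is the baseline in the between-end test, the test carries the variation of removed tissue, in a trial with only 10 pairs.

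**Working it through.** **The plan's own figure.** Section 7.1 claims 80% power for 1.3 SD with a two-sided unpaired t-test at 0.05. With 10 sites per treatment the noncentral t gives 78.5%, so the figure is reproduced to within 2 points. Its unpaired basis, against a paired analysis, is a separate matter and is not used below.

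**Within one site.** Inputs: 10 subjects (Section 3.2), two-sided 0.05. Suppose the drug effect is zero and excision shifts the mean by s SDs of the within-site change. The probability of a significant paired test (noncentral t, 9 df, noncentrality s√10) is:
- s = 1: 80%
- s = 2: about 100%

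The values of s are assumptions. The documents give no lesion volumes, so neither the size nor the direction of the excision shift is known.

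**Between ends: bias.** For each patient let D_post be the TP-end minus base-end difference after surgery, and D_pre the same difference in the old scar. An excision effect common to both ends drops out of both. Treatment is randomized to end, so D_pre has expectation zero, and D_post − D_pre estimates the same treatment effect as D_post. In simulation (100,000 trials, true effect 0.996, equal SDs) the mean was the same with and without subtraction, to within 0.001.

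**Between ends: precision.** Let k = SD(D_pre)/SD(D_post) and r = their correlation. Then

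Var(D_post − D_pre) = SD(D_post)² × (1 + k² − 2rk).

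Subtraction loses precision when 1 + k² − 2rk > 1, that is, when r < k/2.

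Reference effect: with 10 pairs, analysis of D_post alone has 80% power at 0.996 SD of D_post. For the change score that effect becomes 0.996/√(1 + k² − 2rk). Example, k = 1 and r = 0: √2 = 1.414, 0.996/1.414 = 0.704, power 51%. About 18 pairs would then be needed for 80%.

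Power of the change score for the reference effect:

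| k | r = 0 | r = 0.3 | r = 0.5 | r = 0.7 | break-even r |
|---|---|---|---|---|---|
| 0.5 | 71% | 82% | 90% | 96% | 0.25 |
| 1 | 51% | 66% | 80% | 95% | 0.5 |
| 2 | 24% | 30% | 37% | 48% | 1.0 |

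**Adjustment instead of subtraction.** Regress D_post on D_pre and test the intercept at D_pre = 0. The residual SD is SD(D_post) × √(1 − r²), which does not depend on k. The test has 8 df instead of 9 (critical t 2.31 instead of 2.26). Simulated power for the same effect is 74% (r = 0), 78% (r = 0.3), 85% (r = 0.5) and 95% (r = 0.7).

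**The case against.** The best defence is that Section 3.5 lists endpoints, while the planned test is the paired contrast in the Study Summary. Section 3.1 gives the reason for the design: "we plan to treat the same patient with both TP in PCCA PP and PCCA PP alone at different ends of their scar". That stands. A reader might infer from Section 3.5 that the TP-versus-base comparison measures surgery. It does not, since a common excision effect cancels.

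A reader might also infer that subtracting the old scar always adds noise. The documents do not support this. It depends on r < k/2, and they give neither quantity. Section 3.1 even points to a possible lasting site factor, since it randomizes treatment to scar end "to reduce potential bias from distal scar site receiving reduced blood flow compared to proximal scar site". Such a factor could make r positive, and at k = 0.5 a correlation above 0.25 is enough for the change score to gain.

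Two further inferences go beyond the text. On histology, Section 3.5 says only: "Preoperative 5-mm skin biopsy and 4 week postoperative skin biopsy will be used for histological evaluation". It states no comparison or change score for the biopsies. And the repeated-measures ANOVA in the Study Summary uses treatment and follow-up time as factors; nothing places the pre-operative visit among its time levels.

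Collecting pre-operative values is legitimate in itself. They describe the scar that was treated, and they can serve as a covariate.

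What the defence does not remove is that Section 3.5 presents a pre/post comparison as the efficacy signal without naming the contrast, and that the only imaging baseline available for the Study Summary's change is the removed scar.

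**Conclusion.** The point holds in a limited form. The within-site comparison of pre-operative with Week 2 or Week 4 ultrasound cannot show a drug effect, because it includes the excision. This follows from the schedule alone and needs no assumption.

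The paired TP-versus-base comparison of change is unbiased. If the pre-operative value is the one subtracted, which is an inference from reading Section 3.5 with the Study Summary, precision may fall or rise. For an effect with 80% power on post-operative values, change-score power runs from 24% (k = 2, r = 0) to 96% (k = 0.5, r = 0.7). All values of k and r are assumptions. Adjustment keeps power between 74% and 95% over the same correlations, whatever k is, so it is the safer analysis to pre-specify when neither is known.

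Efficacy is a secondary aim in a 10-subject pilot whose primary aim is safety. This should be corrected, but it does not threaten the primary objective.

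**What to change.** In Section 3.5 and the Study Summary:
- Define the ultrasound efficacy contrast as the TP-end minus base-end difference in the post-operative value, at Week 4, with Week 2 supportive.
- Enter the pre-operative between-end difference as a covariate (uncentred, so that the intercept is the treatment effect at zero pre-operative difference). Do not subtract it.
- Report within-site pre- and post-operative values as description only, and state that they include the effect of excision.

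This changes wording only; all the data are already scheduled. The statistical cost is one degree of freedom (critical t 2.26 to 2.31). If the old scar does not predict the new one (r = 0), power is about 6 points lower than in the unadjusted post-operative comparison (74% against 80%). If k is small, the change score could be up to about 5 points better (90% against 85% at k = 0.5, r = 0.5).
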